6.7.1 Stopping Rules

The following stopping rules will be employed during the conduct of this study.

If any of the following stopping rules are met, the study will be paused and no further dosing will occur until the siDMC has reviewed the totality of data available.

1. Any participant dies or requires ICU admission due to SARS-CoV-2 infection.
2. Any participant experiences a serious adverse (SAE) considered related to the vaccine.

3. Any participant experiences any of the following ECIs that are considered as related to the vaccine administration: acute respiratory distress syndrome (ARDS), pneumonitis, acute cardiac injury, arrhythmias, septic shock-like syndrome, acute kidney injury, vasculitis, new onset autoimmune disease, meningitis, atypical measles, encephalitis, or encephalopathy.

If any of the following stopping rules are met, dosing will be paused in the affected Panel, and any other Panels employing the same or higher dose levels, until the siDMC has reviewed the totality of data available. Dosing may continue in Panels receiving lower dose levels while data is reviewed by the siDMC.

4. Grade 3 or higher solicited local AE, considered as related to the vaccine administration reported on 2 or more days within the 5 day post-vaccination period in ≥ 2 participants per panel
5. Grade 3 or higher solicited systemic AE, considered as related to the vaccine administration reported on 2 or more days within the 14 day post-vaccination period in ≥ 2 participants per panel
6. Severe unsolicited AE, considered as related to the vaccine administration within the 28 day post-vaccination period in ≥ 2 participants per panel

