8.4.8.1 Solicited Adverse Event

Solicited AEs for this study are summarized in [Table 6](#).

Table 6 Solicited Adverse Events for Protocol

Type of Solicited Adverse Event	Predefined Solicited Adverse Events	Solicited Time Period
Injection site	
 ○ Injection-site pain/tenderness ○ Injection-site swelling ○ Injection-site redness/erythema 	For the first 5 days after each study intervention 
 ○ For 1-dose panels: Day 1 to Day 5 ○ For 2-dose Day 1 Day 57 panels: Day 1 to Day 5 and Day 57 to Day 61 ○ For 2-dose Day 1 Day 169 panels: Day 1 to Day 5 and Day 169 to Day 173
Systemic	
 ○ Muscle pain/myalgia ○ Joint pain/arthralgia ○ Headache ○ Fatigue/Tiredness ○ Rash ○ Nausea ○ Fever 	For the first 14 days after each study intervention 
 ○ For 1-dose panels: Day 1 to Day 14 ○ For 2-dose Day 1 Day 57 panels: Day 1 to Day 14 and Day 57 to Day 71 ○ For 2-dose Day 1 Day 169 panels: Day 1 to Day 14 and Day 169 to Day 183

All solicited injection-site AEs will be considered related to study intervention. The investigator will assess all solicited injection-site AEs for toxicity, and all solicited systemic AEs for both toxicity and causality (Appendix 3).

In addition, the investigator will review all solicited AEs for the following:

- Is the event a symptom of another diagnosis?
- Is the event ongoing at the end of the solicited period?
- Does the event meet serious criteria?

A solicited AE that meets any of the above criteria must also be reported on the appropriate eCRF as specified in the data entry guidelines.

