10.3.2 Definition of SAE

If an event is not an AE per definition above, then it cannot be an SAE even if serious conditions are met.

An SAE is defined as any untoward medical occurrence that, at any dose:

a. Results in death

b. Is life-threatening

The term “life-threatening” in the definition of “serious” refers to an event in which the participant was at risk of death at the time of the event. It does not refer to an event, which hypothetically might have caused death, if it were more severe.

c. Requires inpatient hospitalization or prolongation of existing hospitalization

Hospitalization is defined as an inpatient admission, regardless of length of stay, even if the hospitalization is a precautionary measure for continued observation. (Note: Hospitalization for an elective procedure to treat a pre-existing condition that has not worsened is not an SAE.) A pre-existing condition is a clinical condition that is diagnosed prior to the use of an MSD product and is documented in the participant’s medical history.

d. Results in persistent or significant disability/incapacity

The term disability means a substantial disruption of a person’s ability to conduct normal life functions.

This definition is not intended to include experiences of relatively minor medical significance such as uncomplicated headache, nausea, vomiting, diarrhea, influenza, and accidental trauma (eg, sprained ankle) that may interfere with or prevent everyday life functions but do not constitute a substantial disruption.

e. Is a congenital anomaly/birth defect

In offspring of participant taking the product regardless of time to diagnosis.

f. Other important medical events

Medical or scientific judgment should be exercised in deciding whether SAE reporting is appropriate in other situations such as important medical events that may not be immediately life-threatening or result in death or hospitalization but may jeopardize the participant or may require medical or surgical intervention to prevent 1 of the other outcomes listed in the above definition. These events should usually be considered serious.

Examples of such events include invasive or malignant cancers, intensive treatment in an emergency room or at home for allergic bronchospasm, blood dyscrasias or convulsions that do not result in hospitalization, or development of drug dependency or drug abuse.

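### Pausing rules 4 and 5 apply their two-day condition to Grade 4 as well as Grade 3, so a related one-day Grade 4 solicited reaction not judged an SAE never counts toward an automatic pause

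*Combined protocol and SAP*

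**What the plan says.** Section 6.7.1 has two groups of rules. Rules 1 to 3 pause the whole study. Rule 2 needs one case: "Any participant experiences a serious adverse (SAE) considered related to the vaccine". Under rules 4 to 6, "dosing will be paused in the affected Panel, and any other Panels employing the same or higher dose levels" until the siDMC has reviewed the data.

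- Rule 4, five-day window, at least two participants per panel: "Grade 3 or higher solicited local AE, considered as related to the vaccine administration reported on 2 or more days".
- Rule 5, 14-day window, at least two participants per panel: "Grade 3 or higher solicited systemic AE, considered as related to the vaccine administration reported on 2 or more days".
- Rule 6, at least two participants per panel, no day count: "Severe unsolicited AE, considered as related to the vaccine administration within the 28 day post-vaccination period".

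Section 7.1 decides whether an individual receives another dose. It sets a duration of more than 24 hours for a related solicited Grade 3 event and no duration for Grade 4. Under Section 8.4.8.1 the investigator asks of every solicited AE: "Does the event meet serious criteria"?

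**The concern.** Requiring persistence is a sensible filter for a short Grade 3 reaction. Rules 4 and 5 carry that filter up to Grade 4, which the grading tables for systemic events and fever label as potentially life threatening. The protocol sets no such condition in Section 7.1, in rule 6, or in the sentinel steps of Section 4.1, and it gives no reason for requiring persistence at Grade 4. As a result, two short severe unsolicited AEs pause a panel, while two one-day Grade 4 solicited reactions do not.

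The people at stake are those not yet dosed. Panels C to F may enrol in parallel, as may G to J. In the single-dose panels (C, D, E, G, H), Section 7.1 has no further dose to withhold, so Section 6.7.1 is the only prespecified automatic protection. Panel E matters most. It gives 10^7 TCID50, above the 10^4 to 10^6 range that Section 4.2.4 reports for MV-CHIK in humans, and 20 of its 25 participants follow the five sentinels.

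**Working it through.** The plan gives no operating characteristics for the pausing rules, so there is no figure to reproduce. The check has two parts: tracing the event through the rules, then an illustration of size.

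**1. Tracing a related, one-day, non-SAE Grade 4 solicited AE**

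| Rule | Requirement | Met? |
|---|---|---|
| 1 | Death or ICU admission from SARS-CoV-2 | No |
| 2 | Related SAE | No, by definition of the case |
| 3 | Closed list of diagnoses (ARDS, vasculitis, encephalitis and others) | No; solicited reactions are not listed |
| 4, 5 | Grade 3 or above on at least two days, in at least two participants | No; one day only |
| 6 | Unsolicited AE | No |

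Any number of such cases in a panel gives no automatic pause. Nor does one such case plus one participant with a two-day Grade 3 reaction.

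**2. Such events can occur**

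Oral temperature above 40.0 °C is Grade 4 (Table 18). An emergency-room visit alone makes an injection-site reaction, headache, fatigue or myalgia Grade 4 (Tables 15 and 16). Neither is automatically serious under Section 10.3.2. The hospitalization criterion needs inpatient admission. On the life-threatening criterion the text says: "It does not refer to an event, which hypothetically might have caused death, if it were more severe". What remains is the important-medical-event criterion, for events that "may jeopardize the participant or may require medical or surgical intervention to prevent 1 of the other outcomes" listed, and that is a judgement.

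A reaction lasting several days with one Grade 4 day may already count, because the toxicity grade is assigned to the AE as a whole. The rule does not say whether each counted day must itself be Grade 3 or above. On either reading, the one-day event is left out.

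**3. Illustration of size**

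Inputs from the documents:
- V591 recipients per panel (Tables 3 and 4): 4 in A and B, 20 in C to L.
- Panel-doses with n = 20: ten at dose 1 (C to L) and five at dose 2 (F, I to L), giving 15.
- Panel-doses with n = 4: A and B, two doses each, giving 4.
- MV-CHIK-202 (Section 4.2.4): 10 of 229 recipients (4.4%; exact 95% CI 2.1 to 7.9%) had a severe solicited AE of any duration. No Grade 4 case is described.

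Assumed, because the documents give neither: p4, the rate per dose of related, one-day, non-SAE Grade 4 solicited AEs, at 0.5%, 1% and 2%; and p3, the rate per dose of two-day Grade 3 events, at 0 or 2%.

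Let T(n, p) = 1 − (1−p)^n − n·p·(1−p)^(n−1), the chance of at least two cases. The added trigger probability per panel-dose is T(n, p3+p4) − T(n, p3).

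Worked example, n = 20, p3 = 0, p4 = 2%: 1 − 0.6676 − 0.2725 = 0.0599. For n = 4 the value is 0.0023. Expected added triggers: 15 × 0.0599 + 4 × 0.0023 = 0.91.

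| p3 | p4 | n = 20 | n = 4 | Both doses, all panels |
|---|---|---|---|---|
| 0 | 0.5% | 0.0045 | 0.0001 | 0.07 |
| 0 | 1% | 0.0169 | 0.0006 | 0.26 |
| 0 | 2% | 0.0599 | 0.0023 | 0.91 |
| 2% | 0.5% | 0.0283 | 0.0013 | 0.43 |
| 2% | 1% | 0.0599 | 0.0028 | 0.91 |
| 2% | 2% | 0.1298 | 0.0068 | 1.97 |

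Sensitivity:
- Dose 1 alone in the ten n = 20 panels, p3 = 2%: 0.28, 0.60 and 1.30.
- Placebo recipients at the same rates (n = 25 or 5, an upper bound), p3 = 2%: 0.61, 1.27 and 2.68. Placebo cases can count, since Section 8.4.8.1 treats every solicited injection-site AE as related.
- Events split equally between rules 4 and 5, pairs only: 0.14 at 1% and 0.51 at 2%.
- Cases accumulated over both doses within a panel, pairs only: 0.39 at 1% and 1.25 at 2%.
- p4 = 0.1%: 0.003 from pairs, 0.08 with p3 = 2%.

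**4. Scope of one pause**

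A trigger in Panel E pauses one panel. A trigger in a 10^6 panel pauses six (B, D, E, H, J, L). A trigger in a 10^5 panel pauses eleven, leaving only Panel F's 10^4 first dose. A trigger after Panel F's first dose pauses all twelve. Panels already fully dosed are unaffected in practice.

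**The case against.** The strongest reply is that this is a choice of threshold, and a defensible one. An emergency-room visit alone produces Grade 4, so the grade partly measures care-seeking. Section 8.3.7 tells participants to seek urgent care for severe suspected-COVID symptoms, and those overlap the solicited systemic list. A day count filters such visits out. Rule 6 covers unanticipated events and uses a severity word that may not match toxicity grade, and Section 7.1 governs one person's next dose, so neither is an exact comparator. The serious cases already meet a stricter rule, since one related SAE stops the study. Grade 3 events are to be reported promptly, solicited events of Grade 3 or above are ECIs, the siDMC reviews data throughout, and the sentinel steps add protection. The assumed rates are not anchored: 2% plus 2% per dose nearly equals the whole 4.4% per recipient seen in MV-CHIK-202. The study has also been terminated.

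Most of this stands, and it limits the weight of the point. It does not close the gap. ECI reporting is not a pause trigger, and outside the sentinels a pause for these events rests on judgement (the siDMC charter is not among the documents). Care-seeking is a good reason to keep the threshold at two related cases. It does not explain why two people with fever above 40.0 °C on one day should not prompt a review.

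**Conclusion.** The concern holds as a low-cost improvement to the design. It is neither an error nor a contradiction, because all the provisions can be followed together. As written, related one-day Grade 4 solicited AEs that are not judged SAEs contribute nothing to the automatic pausing rules, however many occur in a panel. This follows from the text and needs no assumption.

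The practical size does rest on assumptions: binomial counts, independent participants, local and systemic events pooled into one rate, and rates the documents do not supply. On those terms the gap is worth from under 0.1 to about 2 expected triggers over the full planned trial, and close to nothing if one-day Grade 4 events are as rare as 0.1% per dose. Some triggers would fall in panels already fully dosed, where a pause no longer protects anyone in that panel. No objective, endpoint or analysis is affected.

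**What to change.** Limit the two-day condition to Grade 3 in both rules:

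- Rule 4: a related solicited local AE that is either Grade 3 on at least two days or Grade 4 on any day, during the five days after vaccination, in two or more participants in a panel.
- Rule 5: the same for related solicited systemic AEs during the 14 days after vaccination.

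Keep the threshold of two participants, so that a single emergency-room visit does not stop a panel. Leave rule 2 unchanged.

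The cost is one clause per rule and no new data, since these events are already reported as ECIs under Section 8.4.7. The downside is an occasional extra siDMC review, with dosing paused at the same and higher dose levels until it is done. At assumed one-day Grade 4 rates of 1 to 2%, that is about 0.26 to 0.91 expected triggers from pairs alone, or about 0.9 to 2.0 with the assumed 2% Grade 3 rate, and more if placebo cases occur. Since Amendment 04 ends this study, the change is for any later protocol that reuses these rules. A sponsor who prefers to keep the day count should state why a Grade 4 reaction must persist before it counts.

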6.7.2 Delaying Scheduled Study Vaccinations

Study vaccination should be delayed for the following reasons:

- Clinically significant acute illness at the time of vaccination
- Fever (body temperature $\geq 38.0^{\circ}\text{C}$ [100.4°F]) within 24 hours prior to the planned time of vaccination.

6.8 Intervention After the End of the Study

There is no study-specified intervention following the end of the study.

6.9 Clinical Supplies Disclosure

The emergency unblinding call center will use the intervention allocation/randomization schedule for the study to unblind participants and to unmask study intervention identity. The emergency unblinding call center should only be used in cases of emergency (see Section 8.1.10). The Sponsor will not provide random code/disclosure envelopes or lists with the clinical supplies.

This study is blinded but supplies are provided open label; therefore, an unblinded pharmacist or qualified study site personnel will be used to blind supplies. Study intervention identity (name, strength, or potency) is included in the label text; random code/disclosure envelopes or lists are not provided.

See Section 8.1.10 for a description of the method of unblinding a participant during the study should such action be warranted.

7 DISCONTINUATION OF STUDY INTERVENTION AND PARTICIPANT WITHDRAWAL

7.1 Discontinuation of Study Intervention

In clinical trials with a single intervention, discontinuation of study intervention can only occur prior to the intervention and generally represents withdrawal from the study. In this study, participants who receive a single-dose intervention cannot discontinue study intervention.

Discontinuation of study intervention does not represent withdrawal from the study.

As certain data on clinical events beyond study intervention discontinuation may be important to the study, they must be collected through the participant's last scheduled follow-up, even if the participant has discontinued study intervention. Therefore, all participants who discontinue study intervention prior to completion of the protocol-specified vaccination regimen will still continue to participate in the study as specified in Section 1.3 and Section 8.1.9, or if available, a protocol clarification letter.

Participants may discontinue study intervention at any time for any reason or be discontinued from the study intervention at the discretion of the investigator should any untoward effect occur. In addition, a participant may be discontinued from study intervention by the investigator or the Sponsor if study intervention is inappropriate, the study plan is violated, or for administrative and/or other safety reasons. Specific details regarding procedures to be performed at study intervention discontinuation are provided in Sections 8.1.9.

A participant must be discontinued from study intervention but continue to be monitored in the study for any of the following reasons:

The participant or participant's legally acceptable representative requests to discontinue study intervention.

The participant's treatment assignment has been unblinded by the investigator, the Sponsor, or through the emergency unblinding call center.

The participant has a medical condition or personal circumstance which, in the opinion of the investigator and/or Sponsor, placed the participant at unnecessary risk from continued administration of study intervention.

The participant has a confirmed positive serum pregnancy test.

Participant who experiences any of the following events assessed to be related to the product will not receive further vaccination:

- Solicited grade 3 adverse event (AE) for more than 24 hours;

- Unsolicited grade 3 or higher AE;
- Any grade 4 or higher AE; OR
- Serious adverse event (SAE).

For all participants enrolled in 2-dose panels, the inclusion and exclusion criteria should be reviewed prior to the second vaccination. Participants who no longer meet inclusion and exclusion criteria as specified in Section 5.2 will not receive their second scheduled vaccination. If a subject does not receive their second study vaccination, they should still continue all scheduled visits for appropriate safety follow up.

For participants who are discontinued from study intervention but continue to be monitored in the study, see Section 1.3 and Section 8.11.3 for those procedures to be completed at each specified visit.

7.2 Participant Withdrawal From the Study

A participant must be withdrawn from the study if the participant or participant's legally acceptable representative withdraws consent from the study.

If a participant withdraws from the study, they will no longer receive study intervention or be followed at scheduled protocol visits.

Specific details regarding procedures to be performed at the time of withdrawal from the study, as well as specific details regarding withdrawal from future biomedical research, are outlined in Section 8.1.9. The procedures to be performed should a participant repeatedly fail to return for scheduled visits and/or if the study site is unable to contact the participant are outlined in Section 7.3.

7.3 Lost to Follow-up

If a participant fails to return to the clinic for a required study visit and/or if the site is unable to contact the participant, the following procedures are to be performed:

The site must attempt to contact the participant and reschedule the missed visit. If the participant is contacted, the participant should be counseled on the importance of maintaining the protocol-specified visit schedule.

The investigator or designee must make every effort to regain contact with the participant at each missed visit (eg, telephone calls and/or a certified letter to the participant's last known mailing address or locally equivalent methods). These contact attempts should be documented in the participant's medical record.

Note: A participant is not considered lost to follow-up until the last scheduled visit for the individual participant. The missing data for the participant will be managed via the prespecified statistical data handling and analysis guidelines.

8 STUDY ASSESSMENTS AND PROCEDURES

Study procedures and their timing are summarized in the SoA.

Adherence to the study design requirements, including those specified in the SoA, is essential and required for study conduct.

The investigator is responsible for ensuring that procedures are conducted by appropriately qualified (by education, training, and experience) staff. Delegation of study site personnel responsibilities will be documented in the Investigator Trial File Binder (or equivalent).

All study-related medical decisions must be made by an investigator who is a qualified physician.

All screening evaluations must be completed and reviewed to confirm that potential participants meet all eligibility criteria. The investigator will maintain a screening log to record details of all participants screened and to confirm eligibility or record reasons for screening failure, as applicable.

Procedures conducted as part of the participant's routine clinical management (eg, blood count) and obtained before signing of ICF may be utilized for screening or baseline purposes provided the procedure met the protocol-specified criteria and were performed within the time frame defined in the SoA.

Additional evaluations/testing may be deemed necessary by the investigator and or the Sponsor for reasons related to participant safety. In some cases, such evaluation/testing may be potentially sensitive in nature (eg, HIV, Hepatitis C), and thus local regulations may require that additional informed consent be obtained from the participant. In these cases, such evaluations/testing will be performed in accordance with those regulations.

Procedures conducted as part of a site generic screening (with an ERC/IRB approved site generic screening consent) on potential participants (eg, blood count, vital signs, ECG, etc.) and obtained before signing of study ICF may be utilized for screening or baseline purposes provided the procedures met the protocol specified criteria and were performed within the screening window defined in this protocol.

The maximum amount of blood collected from each participant over the duration of the study will not exceed 288 to 441 mL depending on each panel (Appendix 8).

Repeat or unscheduled samples may be taken for safety reasons or for technical issues with the samples.

8.1 Administrative and General Procedures

8.1.1 Informed Consent

The investigator or medically qualified designee (consistent with local requirements) must obtain documented informed consent from each potential participant (or their legally acceptable representative) prior to participating in this clinical study or future biomedical research. If there are changes to the participant's status during the study (eg, health or age of majority requirements), the investigator or medically qualified designee must ensure the appropriate documented informed consent is in place.

